#### Single/First treatment cycle

The safety and tolerability of a single treatment cycle of CLS12311 will be assessed in an ascending dose study across three dose groups involving a total of 9 patients. Patients will be allocated to a low (total dose [REDACTED]; n=2), medium (total dose [REDACTED]; n=3) or high dose (total dose [REDACTED]; n=4)

Each dose group will start with a sentinel patient, who will inform about the safety of the treatment before dosing additional patients. To ensure the safety of dosing in the subsequent patient, a minimum time interval of four days will be established prior to dosing the next patient. This time frame is based on preclinical data showing that peptide-coupled RBCs are fully processed in the first 24h after infusion (see IB 5.3). However, due to the individual manufacturing process of each product and related logistics, only one patient will start treatment per week. Patients who fail to meet the eligibility criteria during screening will be replaced.

The treatment will start with the lowest dose group (2 patients). Higher dose groups (medium dose in 3 patients, high dose in 4 patients) will only be initiated once safety data from the preceding dose group, based on (S)AEs and relapses, has been confirmed by Sponsor's medical

expert(s). The corresponding data should be entered into the eCRF in timely manner, within 24 hours at the latest.

The first patient in each dose group (sentinel patient) will receive a single treatment of CLS12311. Sentinel patients will not receive a second treatment cycle. All sentinel patients will be followed with safety visits until Visit 16 (week 48) according to the schedule of visit (see section 4.1). The safety follow-up of sentinel patients will inform about the safety of the treatment prior to second dosing of other patients.

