#### 16.1.2 Safety Analysis

A comprehensive safety evaluation will be performed after all patients have completed the last scheduled visit.

Safety will be assessed through summaries of exposure to blood donation, study treatment, adverse events, changes in laboratory test results, changes in neurological function, vital signs and MS relapses.

The safety data will be listed and summarized using all safety data available.

Adverse events (AE) will be coded using MedDRA and will be presented by primary System Organ Class (SOC) and Preferred Term. The analysis will focus on the treatment-emergent AEs

(TEAE), i.e. AEs which started or worsened after blood donation for CLS12311 production. The frequency of TEAEs by dose group and in total will be summarized by incidences standardized to the number of patients at risk and rates standardized to the total observation time.

Frequencies of TEAEs by dose group and in total will also be presented by relationship to study treatment and by severity. Additional analyses will be performed for SAE, TESA, AESIs (see section 12.1.1.1), AEs leading to discontinuation.

The number and percentages of patients having experienced a centrally confirmed relapse will be presented by dose group and in total.

Descriptive summaries of observed values and changes from baseline will be presented for hematology and biochemistry variables by dose group. Each abnormal value will be flagged to show whether it is a value below or above the reference range and assessed by the Investigator for clinical relevance. The assessments of laboratory variables will be tabulated by visit for each clinical laboratory analyte by dose group and in total (frequency tables).

The assessment of categorical urinalysis variables will be tabulated by visit for each urine parameter by dose group and in total (frequency tables).

Vital signs will be described by summary statistics (by dose group and in total) for measured values and changes from baseline by visit.

The number and percentages of patients with normal/abnormal findings in physical examinations will be presented by visit (by dose group and in total).

Additional safety analyses will examine the changes in clinical parameters like EDSS, 9-HPT, T25-FW and SDMT.

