4.6 Study Periods

Baseline Phase

The baseline phase will be defined as the period from informed consent signature date to the first blood donation date.

Treatment Phase

The treatment phase will be defined as the period from the date of first blood donation until [REDACTED] ED /EOT.

The treatment phase will be further divided into:

- **Treatment cycle 1:** The period from the date of first blood donation until the day before the second blood donation or the ED visit in case a second blood donation is not performed.
- **Treatment cycle 2:** The period from the date of the second blood donation until [REDACTED] ED /EOT.

Safety Follow-Up Phase

The follow-up period is a period lasting from the end of the treatment phase until study completion or termination date.

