 - AEs for which “Other action taken” is documented as “No further blood donations” or “Patient withdrawn from the trial”
- **TEAEs leading to death:** AEs documented as having a “fatal” outcome.

The intensity or severity of an adverse event is defined according to the Common Terminology Criteria for Adverse Events (CTCAE, version 5.0, 2017) and provided in Table 3.

Table 3 Adverse Event Intensity Classification

Intensity	Explanation
Mild (Grade 1)	
 • Asymptomatic or mild symptoms • Clinical or diagnostic observations only • Intervention not indicated
Moderate (Grade 2)	
 • Moderate, minimal, local or non-invasive intervention indicated limiting age-appropriate instrumental activities of daily living (ADL)
Severe (Grade 3)	
 • Severe or medically significant but not immediately life-threatening; hospitalization or prolongation of hospitalization indicated; disabling symptoms limiting self-care activities of daily living
Life-threatening (Grade 4)	
 • Life-threatening consequences: urgent intervention indicated
Death (Grade 5)	
 • Death related to AE or to multiple sclerosis

AEs of special interest are defined as severe AEs (Grade of ≥ 3) which are related to the IMP and occurring within one day following infusion of CLS12311/placebo: dyspnea, tachycardia, fever, chills, malaise, shock, infection, allergic reaction, renal or liver failure. Adverse events of special interest will be assessed by the investigator.

TEAEs will be summarized using crude and exposure-adjusted incidence rates. A crude incidence rate will be calculated as number of patients with a TEAE divided by number of patients at risk (at the beginning of the study). An exposure-adjusted TEAE incidence rate per 1 patient-year will be defined as number of patients who experienced a TEAE divided by the total time from the blood donation until occurrence of the event for those who experienced an event, or the end of the safety follow-up for those who did not, multiplied by 365.25, among patients at risk at the beginning of the study:

$$I_{AE} = \frac{n}{\sum_i t_i} \times 365.25 = \frac{n}{T} \times 365.25$$

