where n is the total number of patients with the corresponding AE, t_i is equal to the study day of the first corresponding AE for each patient or end of the safety follow-up, T is total time from blood donation until the first event or safety follow-up.

The following statistical output will be provided:

Table 15.2.1.1 Overall Summary of TEAEs – Safety Analysis Set

An overview of TEAEs:

- TEAEs
- Non-serious TEAEs
- Serious TEAEs
- TEAEs related to study treatment or blood donation
- Serious TEAEs related to study treatment or blood donation
- \geq Grade 3 TEAEs
- TEAEs leading to discontinuation
- TEAEs related to study treatment or blood donation leading to discontinuation
- TEAEs leading to death
- TEAEs of special interest

will be displayed by the dose group and overall, for the patients in the SAF.

Table 15.2.1.2.1 Incidence of TEAEs – Safety Analysis Set

Table 15.2.1.2.2 Exposure Adjusted Incidence of TEAEs – Safety Analysis Set

Table 15.2.1.3.1 Incidence of Non-Serious TEAEs – Safety Analysis Set

Table 15.2.1.3.2 Exposure Adjusted Incidence of Non-Serious TEAEs – Safety Analysis Set

Table 15.2.1.4.1 Incidence of Serious TEAEs – Safety Analysis Set

Table 15.2.1.4.2 Exposure Adjusted Incidence of Serious TEAEs – Safety Analysis Set

Table 15.2.1.5.1 Incidence of TEAEs Related to Study Treatment or Blood Donation – Safety Analysis Set

Table 15.2.1.5.2 Exposure Adjusted Incidence of TEAEs Related to Study Treatment or Blood Donation – Safety Analysis Set

Table 15.2.1.6.1 Incidence of Serious TEAEs Related to Study Treatment or Blood Donation – Safety Analysis Set

Table 15.2.1.6.2 Exposure Adjusted Incidence of Serious TEAEs Related to Study Treatment or Blood Donation – Safety Analysis Set

Table 15.2.1.7 Incidence of TEAEs Leading to Discontinuation – Safety Analysis Set

Table 15.2.1.8 Incidence of TEAEs Leading to Death – Safety Analysis Set

Table 15.2.1.9 Incidence of Adverse Events of Special Interest – Safety Analysis Set

Crude and exposure-adjusted incidence rates of TEAEs will be summarized by dose group, SOC and PT. SOC and PTs within each SOC will be ordered by descending number of adverse events in the total column. Tables showing crude incidence rates will be summarized by study period and overall.

Table 15.2.1.10.1 Incidence of TEAEs by Intensity – Safety Analysis Set

Table 15.2.1.10.2 Incidence of TEAEs by Intensity – Modified Safety Analysis Set

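### Read literally, the treatment-cycle-2 columns of most crude TEAE tables are divided by all patients at risk at study start, although only 6 of the 9 planned patients can have a cycle-2 event

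*SAP*

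**What the plan says.** SAP 5.5.1 (Adverse Events) gives one rule for crude incidence: "number of patients with a TEAE divided by number of patients at risk (at the beginning of the study". For the table block that follows it adds: "Tables showing crude incidence rates will be summarized by study period and overall". SAP 4.6 (Study Periods) divides the treatment phase into two cycles. Cycle 1 runs from the first blood donation "until the day before the second blood donation or the ED visit in case a second blood donation is not performed". Cycle 2 is defined as "The period from the date of the second blood donation until" the end of the treatment phase (a redacted visit, ED/EOT). The SAP revision history (Draft 0.4) says that these cycle definitions were added for the adverse-event summaries.

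On who is re-exposed, Protocol 7.1 is explicit: "Sentinel patients will not receive a second treatment cycle". SAP 2.3.1 plans 9 patients in the first cycle (2 low, 3 medium, 4 high) and 6 in the second (1 low, 2 medium, 3 high).

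The main adverse-event tables use the SAF, which SAP 3.1 defines by blood donation and not by infusion. One table differs. Table 15.2.1.10.2 (TEAEs by intensity, modified safety analysis set) is run by treatment-cycle subgroup, and one of those subgroups contains only patients who started both cycles.

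**The concern.** A patient with no second donation cannot have an event in a period that starts at the second donation. Under the stated rule, that patient still counts in the denominator of the cycle-2 column. The percentage is then too low by construction, and the error runs in the reassuring direction. If each patient had the same risk in both cycles, the tables would show that risk falling on re-exposure.

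Safety and tolerability of a second cycle is one of the things the design sets out to assess (Protocol 5.2.3 and 7.1), and period columns invite a comparison of cycle 1 with cycle 2. The tables concerned are 15.2.1.2.1, 15.2.1.3.1, 15.2.1.4.1, 15.2.1.5.1, 15.2.1.6.1, 15.2.1.7 to 15.2.1.9 and 15.2.1.10.1. They include the serious, related, discontinuation and special-interest events, for which no version by treatment-cycle subgroup is planned.

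**Working it through.** **Inputs** (SAP 2.3.1). First cycle: 2 + 3 + 4 = 9 patients. Second cycle: 1 + 2 + 3 = 6 patients. Both sums match the plan's stated totals. The difference, 9 − 6 = 3, is the three sentinels, one per dose group.

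**Formula.** Let x patients have a cycle-2 event, let N be the patients at risk at study start, and let n be the patients who enter cycle 2. The rule prints x/N, whereas the percentage among patients at risk in that period is x/n. The relative understatement is 1 − (x/N)/(x/n) = 1 − n/N, whatever x is. Equivalently, a true per-patient risk p prints as p × n/N.

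| Column | N | n | n/N | Understated by | One affected patient: printed | Among those at risk |
|---|---|---|---|---|---|---|
| Low | 2 | 1 | 0.50 | 50.0% | 1/2 = 50.0% | 1/1 = 100.0% |
| Medium | 3 | 2 | 0.67 | 33.3% | 1/3 = 33.3% | 1/2 = 50.0% |
| High | 4 | 3 | 0.75 | 25.0% | 1/4 = 25.0% | 1/3 = 33.3% |
| Total | 9 | 6 | 0.67 | 33.3% | 1/9 = 11.1% | 1/6 = 16.7% |

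An event in every re-exposed patient would print as 6/9 = 66.7% in the total column, not 100%.

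**If the SAF is larger than 9.** The SAF counts donors. Protocol 9.3.1 provides for additional patients when someone leaves early, and SAP 5.1.1 summarizes repeat enrolments separately. The documents give no final SAF size, so N is an assumption here. With 6 re-exposed patients:
- N = 10: 1 − 6/10 = 40.0%
- N = 11: 1 − 6/11 = 45.5%
- N = 12: 1 − 6/12 = 50.0%

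**The exception.** SAP 5.5.1 says that the intensity tables are summarized as above, which can be read to carry over the split by study period. In the two-cycle subgroup of Table 15.2.1.10.2 the base is the re-exposed patients, planned 6, so N = n and the understatement is zero. That table covers all TEAEs, layered by grade.

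**The case against.** Several points on the other side carry weight.

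- **No denominator is stated specifically for the period columns.** The rule is a general definition, the table shells are separate appendices that are not among the documents, and SAP 4.1 promises a denominator footnote. The shells may already do the right thing. This stands as a limit on certainty. But the only rule in the text gives the wrong base, and a footnote would disclose that without correcting it.
- **The risk of misreading is small at this sample size.** Counts accompany percentages, Table 15.1.11 shows how many patients had a second-cycle infusion, sentinels are flagged in listings, and all adverse events are listed by patient with dates. This stands, and it lowers the severity. It does not justify a wrong percentage.
- **The trial is exploratory, and no endpoint is defined per cycle.** This also stands. The primary and secondary endpoints concern safety overall and by dose group, and the columns not split by period are unaffected.

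A reader might infer more than the documents support:

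- **That every second-cycle percentage is wrong.** Table 15.2.1.10.2 is an exception.
- **That an event recurring on re-exposure is lost.** In the exposure-adjusted rate it is, because that clock stops at the first event ("T is total time from blood donation until the first event or safety follow-up"). In the period tables it is not: SAP 5.5.1 assigns events to periods by onset date, and Protocol 13.2.1 has each occurrence recorded separately.
- **That the protocol requires a rate counting all TEAEs, or a rate per cycle.** Protocol 16.1.2 asks for "rates standardized to the total observation time" but specifies neither. How the exposure-adjusted rate is built is a separate matter.
- **That a completing sentinel's cycle 1 has no end.** SAP 4.6 makes cycle 1 a part of the treatment phase, which ends at ED/EOT, so it is bounded. Only the wording is incomplete.

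**Conclusion.** The point holds for the crude TEAE tables on the SAF. Applied as written, the rule understates cycle-2 percentages by one third in the total column, and by 50%, 33% and 25% in the low, medium and high dose groups. These figures assume the planned 9 and 6 patients and a literal reading of SAP 5.5.1. The one-third figure applies to the total and medium-dose columns only and should not be quoted for the whole table. Donors who were never infused would enlarge it.

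This is a wrong denominator rule, not merely a missing detail. It is limited in reach because the intensity table by treatment-cycle subgroup has the right base in its two-cycle column, and because the overall and dose-group results outside the period split are untouched. It should be fixed, but it does not undermine the trial's stated endpoints.

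**What to change.** In SAP 5.5.1, state that the denominator of each study-period column is the number of patients who entered that period as defined in SAP 4.6. For treatment cycle 2 this means patients with a second blood donation (planned: low 1, medium 2, high 3, total 6). Naming the donation as the entry criterion matters, because SAP 3.2 defines the two-cycle subgroup by infusion and the two counts differ if a second donation is not followed by an infusion. Print that n and the fraction x/n in each column.

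As a secondary wording point, state in SAP 4.6 that cycle 1 ends at EOT or ED for patients without a second donation.

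The cost is SAP wording and a denominator change in the table programs; no new data are needed. If the database is already locked, the SAP Introduction provides for an addendum. The downside is that percentages based on 1 to 3 patients look coarse, which is the precision the data have. An all-event rate or a per-cycle rate is not needed for this fix.

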5.5.2 Multiple Sclerosis Relapse

MS relapse is defined as an appearance of a new neurological abnormality or worsening of previously stable or improving pre-existing neurological abnormality, separated by at least 30 days from onset of a preceding clinical relapse-qualifying event. The abnormality must be present for at least 24 hours and occurred in the absence of fever (< 37.5°C) or known infection.

Severe relapses involve 1) at least one of the following functional systems: motor, cerebellar, brainstem, spinal cord and 2) lead to an increase in EDSS of at least 1 point.

MS relapse assessment will be documented in the eCRF. The following parameters will be collected:

- MS relapse status (resolved/ ongoing)
- Start date
- New neurological abnormality or worsening of previously stable or improving pre-existing neurological abnormality, separated by at least 30 days from onset of a preceding clinical relapse-qualifying event (yes – new/worsening, no)
- Did the symptoms last for at least 24 hours (yes/no)
- Did the symptoms occur in absence of fever or known infection (yes/no)
- Hospitalization status and the reason of hospitalization (patient disability status, routine process for high dose corticosteroid treatment, other therapies as consequence of relapse)
- Plasmapheresis for their MS relapse (yes/no)
- End of symptoms (date (or ongoing), outcome (death, no recovery, complete recovery, partial recovery))
- Short description
- Confirmed relapse by neurological experts (yes/no)
- Meeting criteria for severity as assessed by neurological experts (yes/no)

The following MS relapse parameters will be summarized:

- Patients experiencing an MS relapse according to the investigator
- Patients with centrally confirmed MS relapses
- Patients with severe centrally confirmed MS relapse
- Annualized Relapse Rate (ARR), defined as total number confirmed MS relapses divided by the number of subject-years of post-treatment study participation duration (including the treatment phase and safety follow-up phase):

$$ARR = \frac{\text{number of relapses}}{\text{post – treatment study participation duration (days)}} \times 365.25$$

The following statistical output will be presented:

Table 15.2.2 Summary of MS Relapse – Modified Safety Analysis Set

The number and percentages of patients having experienced a relapse will be presented by visit, dose group and overall. The total number of patients with confirmed relapse and the ARR will be presented by dose group and overall. This summary will be performed by treatment cycle subgroup.

Listing 16.2.4 MS Relapse – Enrolled Analysis Set

MS relapse assessment data will be listed.

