**Withdrawal Criteria**

Patients must be withdrawn from the study under the following circumstances:

- Pregnancy detected at any time during the study. Pregnancy in patients who become pregnant after the first study dose will be followed until delivery. Patients may volunteer further information regarding child health at 12 months after birth
- A positive result in the infectious disease screen analyzed according to local regulations during eligibility testing and/or release of autologous RBC donation.
- The patient withdraws consent
- Patient takes any of the drugs mentioned under exclusion criterion No. 2 (except for relapse treatment as outlined in section 11.2 of the study protocol)
- The patient is unable or unwilling to comply with the protocol
- Any other disease or condition which could interfere with the participation in the study according to the study protocol, or with the ability of the patients to cooperate and comply with the study procedures
- Any medical condition, which the physicians and Investigators deem severe or compromising regarding the safety of the patient and/or the study results, e.g. disease progression requiring the use of effective MS treatment (DMT)

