3.2 Subgroups

The following subgroups will be defined based on their exposure to the IMP:

- **≥ 1 Treatment cycle:** Patients who have initiated at least one treatment cycle (IMP infusion (complete or incomplete) [REDACTED])
- **2 Treatment cycles:** Patients who have initiated both treatment cycles (IMP infusions (complete or incomplete) [REDACTED])

These subgroups will be analysed in disease-related tables (Sections 5.5.2 to 5.5.7).

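### The annualized relapse rate for the '2 Treatment cycles' subgroup pools time and relapses before and after re-dosing, so it cannot be read as the rate after a second cycle

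*SAP*

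**What the plan says.** SAP 5.5.2 gives a single ARR. Its numerator is "defined as total number confirmed MS relapses", with no time window. The count is "divided by the number of subject-years of post-treatment study participation duration (including the treatment phase and safety follow-up phase".

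SAP 4.6 fixes both ends of that period. "The treatment phase will be defined as the period from the date of first blood donation until" the end-of-treatment or early-discontinuation visit, and "The follow-up period is a period lasting from the end of the treatment phase until study completion or termination date".

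For Table 15.2.2, which carries the ARR, the SAP adds: "This summary will be performed by treatment cycle subgroup". SAP 3.2 defines two subgroups. One is everyone who started at least one cycle. The other is "Patients who have initiated both treatment cycles", where an incomplete infusion is enough to count.

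SAP 4.6 also defines separate cycle 1 and cycle 2 periods. The revision history ties these to the adverse event summaries. Section 5.5.2 does not use them.

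**The concern.** A patient joins the '2 Treatment cycles' subgroup by starting cycle 2, but the ARR clock has been running for that patient since the first donation. Nothing in SAP 5.5.2 starts the clock at cycle 2, splits person-time, or limits the numerator to relapses after re-dosing. Relapses and weeks that belong to cycle 1 are therefore reported under the two-cycle label.

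The other column does not help. The subgroup with at least one cycle is in effect the whole mSAF and contains the same re-dosed patients, so the two columns overlap and do not separate one cycle from two.

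The start of the clock is itself unclear. The SAP calls the duration post-treatment and then includes the treatment phase in it. A start at first donation follows from the parenthesis read with SAP 4.6; it is not written as a date.

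This matters because confirmed relapses are a primary safety endpoint (SAP 2.2.1), the safety of a second cycle is a stated aim (SAP 2.3.1), and immune activation with disease exacerbation is a named risk (Protocol 13.4.5). A reader who wants the relapse rate after re-exposure will look at this row.

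**Working it through.** The documents state no ARR, expected relapse count or precision for this analysis, so there is no plan figure to reproduce. The only related arithmetic, 17 + 31 = 48 weeks, is correct.

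**Inputs**
- Planned re-dosed patients: 6 of 9 (SAP 2.3.1).
- Follow-up: 48 weeks per patient (Protocol 15.1).
- Start of cycle 2: redacted. Treatment is planned within 13 weeks of enrolment (Protocol 10.2.4, SAP 5.4). The DSMB reviews a 12-week follow-up after cycle 2 (Protocol 19.1.3); if that is the week 24 visit, cycle 2 falls at about week 12. *Assumed: weeks 11 to 13.* A hard floor is week 7, because week 7 data from a sentinel patient must come first (Protocol synopsis).
- First donation: Visit 2 has no fixed date (schedule of events, footnote 16). *Assumed: weeks 0 to 2.*

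**Share of the denominator before cycle 2**

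Share = (cycle-2 week − donation week) / (48 − donation week).

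| Cycle 2 | Donation | Share |
|---|---|---|
| week 11 | week 2 | 9/46 = 19.6% |
| week 12 | week 0 | 12/48 = 25.0% |
| week 13 | week 0 | 13/48 = 27.1% |
| week 7 (floor) | week 2 to week 0 | 5/46 = 10.9% to 7/48 = 14.6% |

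If the clock began at the first infusion, taken as one week after donation, the range for weeks 11 to 13 would be 17.8% to 25.5%.

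**Person-time, 6 patients, donation at week 0, cycle 2 at week 12**
- Whole study: 6 × 48 × 7 / 365.25 = 5.52 patient-years.
- From cycle 2: 6 × 36 × 7 / 365.25 = 4.14 patient-years.
- Before cycle 2: 5.52 − 4.14 = 1.38 patient-years.

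**ARR per year**

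| Relapses before / after cycle 2 | Plan | From cycle 2 |
|---|---|---|
| 0 / 1 | 1/5.52 = 0.18 | 1/4.14 = 0.24 |
| 0 / 2 | 2/5.52 = 0.36 | 2/4.14 = 0.48 |
| 1 / 1 | 2/5.52 = 0.36 | 1/4.14 = 0.24 |
| 1 / 3 | 4/5.52 = 0.72 | 3/4.14 = 0.72 |

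The plan's figure is below the post-cycle-2 rate only when the rate before cycle 2 is lower than the rate after it. At week 12 the time splits 1:3, so the two agree when there are three relapses after re-dosing for each one before. For the 0 / 1 case, moving cycle 2 to week 11 or week 13 gives 0.235 or 0.248 in the last column.

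**The case against.** **The rate need not be biased.** Relapses before cycle 2 are counted along with the time before it. With a constant relapse rate and no selective loss, the plan's ARR is unbiased. This stands. A reader might infer that the reported rate is simply too low by the share of time that precedes cycle 2; that is true only if every relapse falls after re-dosing.

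**The early time is not event-free.** A reader might also infer that patients had to stay relapse-free to enter the subgroup. The documents do not say so. Relapse is not among the reasons in Protocol 14.5 for withholding the next infusion, and Protocol 11.2 only postpones the visit until steroid treatment ends. Three of nine patients stay out by design, as sentinels. Two relapse-linked routes out remain: withdrawal for "disease progression requiring the use of effective MS treatment (DMT"), and a DSMB recommendation to stop further treatment, for which a severe confirmed relapse within 4 weeks of dosing triggers a meeting. Selective loss is therefore possible, but nothing shows that it occurs or how often.

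**Relapse timing is visible elsewhere.** Table 15.2.2 also gives relapses by visit. Listing 16.2.4 covers the relapse data, for which a start date is collected, and Listing 16.2.2.2 covers infusions. With nine planned patients a careful reader can place each relapse. This stands, but it does not repair the printed rate.

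**The ARR is descriptive and imprecise.** It is not a protocol endpoint, there are no formal hypotheses, and SAP 3.2 never says that the subgroups contrast one cycle with two. For a single relapse the exact 95% Poisson interval is about 0.005 to 1.01 per year on 5.52 patient-years and 0.006 to 1.35 on 4.14. The difference between 0.18 and 0.24 is well inside that noise. This limits the weight of the point; it does not make the label right.

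**Conclusion.** The point holds as one of definition and labelling. The ARR for the '2 Treatment cycles' subgroup mixes experience before and after re-dosing and cannot be read as the relapse rate after a second cycle. About 20% to 27% of its denominator precedes cycle 2, on the assumption of cycle 2 at weeks 11 to 13 and first donation at weeks 0 to 2 of 48. The true weeks are redacted and treatment may be postponed, so this is an inference.

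The direction of the error is not fixed. The documents do not support calling the rate systematically too low, nor treating the early time as guaranteed free of relapses. The correction is worth making because it is cheap, changes a printed rate on a primary safety endpoint, and resolves a start date that the SAP leaves contradictory. It would not be expected to change a conclusion on numbers this small.

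**What to change.** In SAP 5.5.2:

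1. State the ARR start date explicitly and remove the conflict between a post-treatment duration and one that includes the treatment phase.
2. Replace the subgroup ARR with two rows, split at the first cycle-2 infusion: (a) from the first IMP infusion to the day before the first cycle-2 infusion, or to end of study, for all mSAF patients; (b) from the first cycle-2 infusion, for re-dosed patients only. Count each relapse in the row that contains its start date.
3. Keep the whole-study ARR for the mSAF total only.
4. Show events and patient-years beside each rate, and present the rows descriptively.

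Two notes belong under the table. First, sentinels supply most of row (a). With cycle 2 at week 12, and ignoring the lag from donation to infusion, they give 3 × 48 = 144 of 144 + 6 × 12 = 216 patient-weeks, about two thirds. Row (a) against row (b) is therefore not a clean contrast of one cycle with two. Second, the split date differs from the cycle-2 period in SAP 4.6, which starts at the second donation.

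Infusion dates (SAP 5.4) and relapse start dates (SAP 5.5.2) are already in the eCRF, so the work is a paragraph of SAP text and a revised shell for Table 15.2.2, or an SAP Addendum if the database is locked. The downside is less person-time per row: on the same assumptions each row has 216 patient-weeks, or 4.14 patient-years, against 9 × 48 × 7 / 365.25 = 8.28 for the mSAF total.
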